12.1.12.5. Immunological/Inflammation Assessments

IL-6, C-reactive protein (CRP), ferritin, D-dimer, and procalcitonin (tested locally) will be measured as biomarkers of CRS as indicated in the Table of Events, [Section 7 Table 3](#).

Note: CRS management and grading relies primarily on clinical signs and symptoms, these laboratory measurements will be collected as biomarkers to support CRS diagnosis/monitoring.

12.1.12.6. Pregnancy Screen

Pregnancy test is required for all female subjects of childbearing potential. Serum or urine beta human chorionic gonadotropin (β -hCG) pregnancy test will be performed at Screening and at Day 28. Negative results are required for CYNK-001 administration to be initiated.

12.1.12.7. Exploratory laboratory testing

Please refer to [Section 13](#) for more information on these assessments.

12.1.12.8. Urinalysis

Urinalysis (dipstick) will be assessed if clinically indicated as outlined in the Table of Events, [Section 7, Table 3](#).

12.2. Best Supportive Care Treatment

Subjects are expected to receive best supportive care as defined by the institution during the course of this study starting Day 1. The specific medication and duration of therapy is at the discretion of the treating physician. These medications must be documented in the source documents as treatment for COVID-19.

12.3. Adverse and Serious Adverse Events

12.3.1. Definition of Adverse Events

12.3.1.1. Adverse Event (AE)

An AE is the development of an undesirable medical condition or the deterioration of a pre-existing medical condition following or during exposure to a pharmaceutical product, whether or not considered causally related to the product. In clinical studies, an AE can include an undesirable medical condition occurring at any time, including baseline or washout periods, even if no study treatment has been administered.

An AE is any noxious, unintended, or untoward medical occurrence that may appear or worsen in a subject during the course of a study. It may be a new intercurrent illness, a worsening concomitant illness, an injury, or any concomitant impairment of the subject's health, including laboratory test values, regardless of etiology. Any worsening (i.e., any clinically significant adverse change in the frequency or intensity of a pre-existing condition) should be considered an AE. A diagnosis or syndrome should be recorded on the AE page of the eCRF rather than the individual signs or symptoms of the diagnosis or syndrome.

Abuse, withdrawal, sensitivity or toxicity to an investigational product should be reported as an AE. Overdose, accidental or intentional, whether or not it is associated with an AE should be reported on the overdose eCRF. (See [Section 9.1.2](#) for the definition of overdose.) Any sequela of an accidental or intentional overdose of an investigational product should be reported as an AE on the AE eCRF. If the sequela of an overdose is an SAE, then the sequela must be reported on an SAE report form and on the AE eCRF. The overdose resulting in the SAE should be identified as the cause of the event on the SAE report form and eCRF but should not be reported as an SAE itself.

In the event of overdose, the subject should be monitored as appropriate and should receive supportive measures as necessary. There is no known specific antidote for CYNK-001 overdose. Actual treatment should depend on the severity of the clinical situation and the judgment and experience of the treating physician.

All subjects will be monitored for AEs during the study. **Infusion related reactions (IRRs) will be documented for the first 72 hours of CYNK-001 infusion at every dose.** Assessments may include monitoring of any or all of the following parameters: the subject's clinical symptoms, laboratory, pathological, radiological or surgical findings, physical examination findings, or findings from other tests and/or procedures.

All AEs that occur after any subject has been enrolled, before treatment, during treatment, or within 28 days following the first CYNK-001 infusion (to Study Day 28), whether or not they are related to the study, must be recorded on forms provided by Celularity.

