12. ASSESSMENT OF SUBJECTS

12.1. Study Activities and Evaluations

Subject safety will be assessed in all subjects who receive any amount of CYNK-001 and will include AEs, vital signs, body weight measurements, physical examination findings, clinical laboratory test results, infusion site assessments, x-ray or computerized tomography (CT) scan results, electrocardiogram (ECG) interpretations, electroencephalography (EEG) if clinically indicated, pregnancy testing for FCBP, and concomitant medications and procedures will be tabulated and summarized by cohort. Timing of evaluations will be assessed as outlined in the Table of Events, [Section 7 Table 3](#).

All AEs will be reported and recorded in the electronic case report form (eCRF). For serious adverse events (SAEs), an expedited reporting procedure will be used. The rate of AEs, SAEs, abnormal laboratory AEs and vital signs (graded according to the NCI CTCAE Version 5.0) will be measured while the subject is on study.

The ASTCT Consensus Grading for CRS and Neurologic Toxicity Associated with Immune Effector Cells will be used for the purposes of grading of CRS considered associated with CYNK-001 by the Investigator. CRS Grading can be found in [Section 12.6.2](#). Any new CRS event or worsening of a pre-existing CRS event at any grade is an expected event and immediately reportable.

Subjects will be monitored for safety from the time of signing ICF through end of study and will be collected in the eCRF.

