12.3.1.7. Severity/Intensity

For both AEs and SAEs, the Investigator must assess the severity/intensity of the event.

The severity/intensity of AEs will be graded based upon the subject’s symptoms according to the current active minor version of the Common Terminology Criteria for AEs (CTCAE, version 5.0);

https://ctep.cancer.gov/protocoldevelopment/electronic_applications/ctc.htm

Following CYNK-001 infusion, AEs will be included up to Day 28 post first CYNK-001 infusion. Subjects will be monitored for AEs throughout the study. Importantly, the symptoms associated with the subject’s CRS should be captured independently from the CRS designation and graded using CTCAE, version 5.0 to facilitate greater understanding of CRS associated with CYNK-001.

The AEs that are not defined in the CTCAE should be evaluated for severity/intensity according to the following scale:

- Grade 1 = Mild – transient or mild discomfort; no limitation in activity; no medical intervention/therapy required
- Grade 2 = Moderate – mild to moderate limitation in activity, some assistance may be needed; no or minimal medical intervention/therapy required
- Grade 3 = Severe – marked limitation in activity, some assistance usually required; medical intervention/therapy required, hospitalization is possible
- Grade 4 = Life-threatening – extreme limitation in activity, significant assistance required; significant medical intervention/therapy required, hospitalization or hospice care probable
- Grade 5 = Death - the event results in death

The term “severe” is often used to describe the intensity of a specific event (as in mild, moderate or severe myocardial infarction); the event itself, however, may be of relatively minor medical significance (such as severe headache). This criterion is not the same as “serious” which is

based on subject/event outcome or action criteria associated with events that pose a threat to a subject's life or functioning.

Seriousness, not severity, serves as a guide for defining regulatory obligations.

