12.4. Reporting of Serious Adverse Events

Any AE that meets any criterion for an SAE requires the completion of an SAE Report Form in addition to being recorded on the AE page/screen of the eCRF. All SAEs must be reported to Drug Safety within 24 hours of the Investigator's knowledge of the event by facsimile, or other appropriate method (e.g., via email), using the SAE Report Form, or approved equivalent form. This instruction pertains to initial SAE reports as well as any follow-up reports.

The Investigator is required to ensure that the data on these forms is accurate and consistent. This requirement applies to all SAEs (regardless of relationship to CYNK-001) that occur during the study (from the time the subject signs Study ICF until Study Day 28) or any SAE made known to the Investigator at any time thereafter that are suspected of being related to CYNK-001. SAEs occurring prior to treatment (Screening Period) will be captured in the EDC.

The SAE report should provide a detailed description of the SAE and include a concise summary of hospital records and other relevant documents. If a subject died and an autopsy has been performed, copies of the autopsy report and death certificate are to be sent to Drug Safety as soon as these become available. Any follow-up data should be detailed in a subsequent SAE Report Form, or approved equivalent form, and sent to Drug Safety.

Where required by local legislation, the Investigator is responsible for informing the Institutional Review Board/Ethics Committee (IRB/EC) of the SAE and providing them with all relevant initial and follow-up information about the event. The Investigator must keep copies of all SAE information on file including correspondence with Celularity and the IRB/EC.

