12.6. Potential Risks and Management of Treatment Toxicities

12.6.1. Graft Versus Host Disease (GvHD) Target Organ Staging

AEs that are related to GvHD should be monitored for at least 100 days after last CYNK-001 infusion and evaluated for severity/intensity according to guidelines outlined by the Mount Sinai Acute GvHD International Consortium as outlined in [Table 6 \(Harris, 2016\)](#).

Table 6: GvHD Staging

Stage	Skin (Active Erythema Only)	Liver (Bilirubin)	Upper Gastrointestinal (GI)	Lower Gastrointestinal (GI) (stool output/day)
0	No active (erythematous) GvHD rash	< 2 mg/dL	No or intermittent nausea, vomiting, or anorexia	< 500 mL/day or < 3 episodes/day
1	Maculopapular rash < 25% body surface area	2 to 3 mg/dL	Persistent nausea, vomiting, or anorexia	500-999 mL/day or 3 to 4 episodes/day
2	Maculopapular rash 25% to 50% body surface area	3.1 to 6 mg/dL		1000 to 1500 mL/day or 5 to 7 episodes/day
3	Maculopapular rash > 50% body surface area	6.1 to 15 mg/dL		> 1500 mL/day or > 7 episodes/day
4	Generalized erythroderma (> 50% body surface area) plus bullous formation and desquamation > 50% body surface area	> 15 mg/dL		Severe abdominal pain with or without ileus or grossly bloody stool (regardless of stool volume)

Source: [Harris, 2016](#)

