14.1 Adverse Events

All AEs will be coded using the MedDRA dictionary Version 23.0 or higher. The severity of toxicities for AEs will be graded 1 to 5 according to the National Cancer Institute Common Terminology Criteria for Adverse Events (NCI-CTCAE) Version 5.0 whenever possible. AEs with missing severity will be presented in the summary table as missing category.

A treatment-emergent adverse event (TEAE) is defined as an AE which started on or after the first dosing date of the study drug or an existing condition being worse on or after the first dosing date of the IP.

Adverse events with unknown onset date and with end date after first dosing date will be counted in the TEAE.

A treatment-related AE is defined as an AE which is considered to be of suspected relationship to the study drug. Adverse events with missing relationship to study drug will be assessed as treatment-related.

The following summaries will be provided:

- A table for overall summary and a listing of all AEs by SOC and PT will be provided for AEs that occurred during the screening period.
- Separate summaries will be provided for the treatment period (Day 1 – Day 28) and follow-up period (Day 29 to 6 months). The following summary tables will be generated:
 - Overall summary
 - All TEAEs by SOC and PT
 - TEAEs that satisfy the DLT criteria (Phase I treatment period only)
 - TEAEs leading to discontinuation of treatment
 - TEAEs with toxicity grade ≥ 3
 - Drug-related TEAEs
 - Serious TEAE
 - TEAEs that led to death
 - Summary of CRS

If a subject experiences multiple AEs under the same PT (SOC), then the subject will be counted only once for that PT (SOC). If a subject experiences the same AE more than once with different toxicity grade, the event with the highest grade will be tabulated in “by maximum toxicity grade” tables.

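### The protocol gives conflicting end dates for adverse-event recording, so the SAP's tables for Day 29 to 6 months may be incomplete for non-serious events, including non-serious GvHD

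*Protocol*

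**What the plan says.** The documents describe the period after Day 28 in several ways.

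- Protocol 12.3.1.1: adverse events arising "within 28 days following the first CYNK-001 infusion (to Study Day 28), whether or not they are related to the study, must be recorded". The count starts at the first dose.
- Protocol 12.3.1.7: "AEs will be included up to Day 28 post first CYNK-001 infusion". The next sentence there says monitoring continues throughout the study.
- Protocol 12.1: "Subjects will be monitored for safety from the time of signing ICF through end of study and will be collected in the eCRF". The same section says all adverse events go into the eCRF, with no time limit.
- Protocol 12.3.1.2: every SAE after any amount of CYNK-001 is to be recorded, with no end date.
- Protocol 12.4: SAEs are reported to Drug Safety until Study Day 28 whatever their cause. After that the duty covers "any SAE made known to the Investigator at any time thereafter that are suspected of being related to CYNK-001".
- Protocol 12.6.1: "AEs that are related to GvHD should be monitored for at least 100 days after last CYNK-001 infusion".
- Protocol Table 2: Phase I DLTs are assessed to Day 28; the Phase II safety endpoint has a Month 6 timeframe.
- SAP 14.1: one set of summaries for Days 1 to 28 and another for the "follow-up period (Day 29 to 6 months". The listed tables include all TEAEs, Grade 3 or above, drug-related, serious and fatal events. Only the DLT table is confined to the Phase I treatment period.

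**The concern.** The rule with an explicit cut-off for general adverse events is the Day 28 rule, stated twice. A site could reasonably stop entering non-serious events then, while another site following 12.1 would carry on. The SAP tabulates the later period as if recording were complete.

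GvHD shows what is at stake. CYNK-001 is an allogeneic cell product, and the protocol itself asks for at least 100 days of GvHD monitoring. A non-serious skin or gut GvHD event starting on Day 45 would be monitored under 12.6.1 but need not be recorded under 12.3.1.1. It could then be missing from a table presented as all follow-up TEAEs. A reader of a sparse or empty table could not tell whether nothing happened or nothing had to be written down.

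**Working it through.** The plan states no figure to reproduce; the check compares time windows.

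**Inputs**
- Study Day 1 is the first dose (SAP 12).
- Infusions are planned for Days 1, 4 and 7 (Protocol 6.1.2); the Table of Events allows the third dose up to 2 days late, so Day 9.
- General recording limit: Study Day 28 (12.3.1.1).
- GvHD monitoring: at least 100 days after the last infusion (12.6.1).
- Follow-up visits: Day 90 ± 14 and Day 180 ± 14 (Table of Events).

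**Formulas**
- Last day of GvHD window = last-dose day + 100
- Days of the window inside the Day 28 rule = 28 − last-dose day
- Days outside it = (last-dose day + 100) − 28

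| Last dose | Window ends | Inside Day 28 rule | Outside |
|---|---|---|---|
| Day 1 | Day 101 | 27 | 73 |
| Day 4 | Day 104 | 24 | 76 |
| Day 7 | Day 107 | 21 | 79 |
| Day 9 | Day 109 | 19 | 81 |

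For a Day 7 last dose, 107 − 28 = 79 of the 100 days (Days 29 to 107) fall outside the dated rule. One ambiguity is small: under the SAP's day count, 28 days after Day 1 is Study Day 29, whereas the protocol's bracket says Study Day 28. Using Day 29 gives 107 − 29 = 78.

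**SAP follow-up table.** Taking 6 months as Day 180, Days 29 to 180 are 180 − 29 + 1 = 152 of 180 study days (84%). All of them lie beyond the Day 28 rule.

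**Which events are affected**
- Serious events: 12.3.1.2 requires them to be recorded without an end date. Section 12.4 narrows reporting after Day 28 to suspected-related SAEs, so these two sections also need reconciling, but serious events are not left without a recording duty.
- Non-serious events, including non-serious GvHD: required by 12.1, outside the limit in 12.3.1.1 and 12.3.1.7. The gap lies here.

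**Visits.** The Day 90 window runs from Day 76 to Day 104 (90 ± 14) and the Day 180 window from Day 166 to Day 194. Daily telephone contact after discharge is required only through at least the Day 15 visit. The visible schedule has no visit column between Day 28 (+2) and Day 76, apart from the discharge and early-termination columns. The adverse-event rows and follow-up footnote of the Table of Events are not shown, so what is collected at these visits cannot be verified.

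**The case against.** A reader might infer that nothing after Day 28 has to be recorded, and that the late-toxicity tables will therefore look clean. The documents do not support this. Section 12.1 calls for eCRF collection to the end of the study, 12.3.1.1 itself says "All subjects will be monitored for AEs during the study", and 12.3.1.2 keeps all SAEs recordable. The hidden rows of the Table of Events may also require adverse-event collection at Days 90 and 180. Incompleteness is therefore possible, not certain, and confined to non-serious events.

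Two further inferences go too far.
- The Day 90 window closes on Day 104, before Day 107, but 12.6.1 asks for monitoring and not for a visit on the hundredth day. The Day 180 visit can pick up onset since the last contact.
- A last dose as late as Day 11 would need two successive delays, a combination that section 6.5 does not state. Day 9 is the supported upper bound.

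The practical reach is also limited. The Month 6 safety timeframe in Table 2 belongs to Phase II, which was not run; SAP 15 records closure after 7 subjects in Phase I.

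What stands after all this is that the sections disagree and nothing says which governs. SAP 15 keeps adverse-event summaries for those 7 subjects, and in a group that small one unrecorded event changes a table noticeably (1/7 = 14%).

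**Conclusion.** The conflict is real and should be fixed, though it is not critical. Protocol 12.1, 12.3.1.1, 12.3.1.2, 12.3.1.7, 12.4 and 12.6.1 do not agree on when recording ends, and SAP 14.1 tabulates a period in which the dated rule has lapsed. On the assumption that a site follows 12.3.1.1, non-serious events carry no recording duty for 79 of the 100 days after a Day 7 last dose (73 to 81 days for last doses on Days 1 to 9). The follow-up tables may then be incomplete for non-serious events. The size of any under-count cannot be estimated: it depends on which section sites followed and on what the eCRF required at Days 90 and 180. For the trial as closed, the consequence is confined to the adverse-event summaries of the 7 dosed Phase I subjects.

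**What to change.** 1. Reconcile Protocol 12.1, 12.3.1.1, 12.3.1.2, 12.3.1.7, 12.4 and 12.6.1 with Table 2 and SAP 14.1 on a single end date for recording, and keep that distinct from the rule for reporting SAEs to Drug Safety.
2. At minimum, require GvHD-related events to be entered in the eCRF for the whole period that 12.6.1 already sets, counted from the last infusion. Capture onset since the last contact at the existing Day 90 and Day 180 visits.
3. If general recording does end at Day 28, restrict and title the SAP 14.1 follow-up tables by what had to be recorded: all SAEs, GvHD-related events and deaths. Limiting them to suspected-related SAEs would wrongly drop the unsuspected SAEs that 12.3.1.2 requires.
4. For the 7 dosed subjects, state in the brief study report which events sites were required to record after Day 28, and title any follow-up summaries to match.

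The cost is protocol and SAP wording, eCRF adverse-event pages left open at two existing visits, and a few more entries in follow-up. No new visits and no change to treatment are needed. For the subjects already dosed, the labelling costs almost nothing.

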12.3.1.2. Serious Adverse Event (SAE)

A SAE is an AE occurring during the conduct of the study, and at any dose of the investigational product that fulfils one or more of the following:

- Results in death
- It is immediately life-threatening
- It requires in-patient hospitalization or prolongation of existing hospitalization
- It results in persistent or significant disability or incapacity
- Results in a congenital abnormality or birth defect
- It is an important medical event that may jeopardize the subject or may require medical intervention to prevent one of the outcomes listed above.

All SAEs that occur after any amount of treatment with CYNK-001, must be recorded on forms provided by Celularity.

Events **not considered** to be SAEs are hospitalizations for:

- a standard procedure for protocol therapy administration. However, hospitalization or prolonged hospitalization for a complication of therapy administration will be reported as an SAE.
- routine treatment or monitoring of the studied indication not associated with any deterioration in condition.
- the administration of blood or platelet transfusion as routine treatment of studied indication. However, hospitalization or prolonged hospitalization for a complication of such transfusion remains a reportable SAE.
- a procedure for protocol/disease-related investigations (e.g., surgery, scans, endoscopy, sampling for laboratory tests, bone marrow sampling). However, hospitalization or prolonged hospitalization for a complication of such procedures remains a reportable SAE.
- hospitalization or prolongation of hospitalization for technical, practical, or social reasons, in absence of an AE.
- a procedure that is planned (i.e., planned prior to start of treatment on study); must be documented in the source document and the eCRF. Hospitalization or prolonged hospitalization for a complication remains a reportable SAE.
- an elective treatment of or an elective procedure for a pre-existing condition, unrelated to the studied indication, that has not worsened from baseline.
- emergency outpatient treatment or observation that does not result in admission, unless fulfilling other seriousness criteria above.

If an AE is considered serious, both the AE page/screen of the eCRF and the SAE Report Form must be completed.

For each SAE, the Investigator will provide information on severity, start and stop dates, relationship to the CYNK-001, action taken regarding the CYNK-001, and outcome.

12.3.1.3. Suspected Unexpected Serious Adverse Drug Reaction (SUSAR)

SUSAR is an adverse drug reaction that is both serious and unexpected (per the IB) which, based on the opinion of the investigator and/or sponsor, is felt to have a reasonable suspected causal relationship to an investigational product.

12.3.1.4. Anticipated Event

Adverse experiences (serious or non-serious) that commonly occur in the study population or background regimen. Such events include known consequences of the underlying disease (disease-related) or condition under investigation (e.g., symptoms, disease progression) and events unlikely to be related to the underlying disease or condition under investigation but common in the study population independent of drug therapy (e.g., non-acute death observed in a trial with cancer patients). For reporting purposes, anticipated events are not “expected” because they are not listed in the IB.

